5.1.2. Secondary Objective(s)

The secondary objectives are to assess safety, to measure durability of complete response during long-term follow-up, and to measure overall ESCC progression and associated mortality after treatment.

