5.2.2. Secondary Endpoint(s)

1. The percentage of subjects with a sustained CR during long-term follow-up, defined as patients with a CR at 12 months that sustained this absence of squamous abnormalities (MGIN or worse) during all subsequent FU endoscopies through 60 months.
2. Proportion of patients with CR after primary RFA, defined as absence of MGIN or worse in any of the biopsies from the treatment area, at the three month visit.
3. Proportion of patients demonstrating progression within the treatment area (TA), defined as detection of ESCC in biopsy or resection specimen at any time within the first 12 months.
4. Occurrence of serious adverse device effects (SADE) after RFA treatment.
5. Proportions of “run-in” subjects, are defined as the first 5 subjects enrolled per endoscopist that is inexperienced with RFA or has had no RFA onsite training from CICAMS, with a CR at 3 and 12 months after the initial treatment session, and with sustained CR during follow-up.
6. Proportion of patients with CR at 12 months who subsequently developed recurrent disease in TA, defined as MGIN or HGIN for patients with MGIN at baseline, and MGIN or HGIN for patients with HGIN at baseline.
7. Proportion of patients with CR at 12 months who subsequently developed progressive disease in TA, defined as ESCC in biopsy or resection specimen.
8. Durability after reiterative RFA, defined as proportion of patients with a CR at 12 months who sustain or re-establish CR upon reiterative RFA treatment sessions during FU.
9. Durability after additional endoscopic treatment, defined as proportion of patients with CR at 12 months who sustain or re-establish CR upon endoscopic treatment (RFA and eventually in combination with EMR or ESD) during FU.
10. Esophageal squamous cell cancer mortality.
11. Proportion of patients demonstrating MGIN or worse outside the TA during treatment phase or follow-up.

6. Study Design

This clinical study will evaluate a subject population having macroscopically flat type (type 0-IIb) esophageal lesions with histological evidence of MGIN or HGIN in biopsy specimens obtained from the esophagus.

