Although preliminary, results for the long-term follow-up of this study will be shortly discussed. Sustained CR during 5 years follow-up was observed in 86% (67/78 patients). Recurrence occurred in 9% (7/78 patients, MGIN 5, HGIN 1). 5 were managed with RFA, one with ESD. Progression of baseline disease occurred in another 5% (4/78 patients; HGIN (n=1), sm-ESCC (n=3)); all were treated with ESD. Two progressor lesions were normally stained after Lugol's and with repeatedly negative biopsies, and were therefore left untreated. Later both lesions were considered suspicious for cancer and escape treatment was performed, with pathology assessment for one case showed submucosal cancer buried under normal epithelial cells. Pathology assessment for the second case is pending.

However, protocol violations during follow-up occurred in the majority of patients (59%) resulting in prolonged follow-up intervals, lesions left untreated or no adequate follow-up after detection of recurrent or progressive disease. This might have interfered with the results, and those might have been better with strict follow-up protocols.

The 12 patients with residual ESCN suffered a poorer prognosis. Fifty-eight percent (7/12 patients) developed progressive disease and were treated with either ESD (n=2) or non-endoscopic treatment (n=5), suggesting that RFA failures should directly be managed with an alternative treatment like EMR or ESD.

Therefore, to further assess the safety, effectiveness, and durability of the Barrx™ Flex Radiofrequency Ablation System for the eradication of ESCN, the current study will employ methods similar to the 2 studies reported above but with a consistent primary RFA dose of 12 J/cm² with one application and no cleaning of the coagulum, and with subsequent 5-years follow-up according to strict study protocols.

7. Product Description

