Patients with residual ESCN at 12 months will be defined as treatment failures, and will undergo escape treatment within 3 months (+/- 4 weeks). If CR will be re-established after escape treatment, patients will stay in the trial and will be followed-up and treated if necessary, according to figure 2. If non-endoscopic treatment is performed at 12 months, or if pathology indicates non-endoscopic treatment, patients won't be treated and/or followed-up according to the study protocol, but will still be followed-up until 5 years after baseline to assess secondary endpoints.

[figure not shown]

Figure 1. Decision Tree for Subject Flow Through in Treatment Phase (adapted from He et al., 2014 (18))

[figure not shown]

Figure 2. Decision Tree for Subject Flow in Follow-Up Phase (adapted from He et al., 2014 (18))

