7.9.2. Secondary Endpoint(s)

1. The percentage of subjects with a sustained CR during long-term follow-up, defined as patients with a CR at 12 months that sustained this absence of squamous abnormalities (MGIN or worse) during all subsequent FU endoscopies through 60 months.
2. Proportion of patients with CR after primary RFA, defined as absence of MGIN or worse in any of the biopsies from the treatment area, at the three month visit.
3. Proportion of patients demonstrating progression within the treatment area (TA), defined as detection of ESCC in biopsy or resection specimen at any time within the first 12 months.
4. Occurrence of serious adverse device effects (SADE) after RFA treatment.
5. Proportions of "run-in" subjects, defined as the first 5 subjects enrolled per endoscopist, with a CR at 3 and 12 months after the initial treatment session, and with sustained CR during follow-up.

This document is electronically controlled. Printed copies are considered uncontrolled.

Confidential

12JUL2017

6. Proportion of patients with CR at 12 months who subsequently developed recurrent disease in TA, defined as MGIN or HGIN for patients with MGIN at baseline, and MGIN or HGIN for patients with HGIN at baseline.
7. Proportion of patients with CR at 12 months who subsequently developed progressive disease in TA, defined as ESCC in biopsy or resection specimen.
8. Durability after reiterative RFA, defined as proportion of patients with a CR at 12 months who sustain or re-establish CR upon reiterative RFA treatment sessions during FU.
9. Durability after additional endoscopic treatment, defined as proportion of patients with CR at 12 months who sustain or re-establish CR upon endoscopic treatment (RFA and eventually in combination with EMR or ESD) during FU.
10. Esophageal squamous cell cancer mortality.
11. Proportion of patients demonstrating MGIN or worse outside the TA during treatment phase or follow-up.

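### The objective is overall ESCC progression, but no progression endpoint counts ESCC in the treatment area first found after month 12 in patients without complete response

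*Protocol*

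**What the plan says.** One secondary objective (CIP 5.1.2, repeated in SAP 4.2) is "to measure overall ESCC progression and associated mortality after treatment". It is not limited by 12-month response or by time.

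Two secondary endpoints in CIP 5.2.2 measure progression in the treatment area (TA):

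- No. 3 takes all patients, but only "detection of ESCC in biopsy or resection specimen at any time within the first 12 months".
- No. 7 takes the later period, but only as the "Proportion of patients with CR at 12 months who subsequently developed progressive disease in TA, defined as ESCC in biopsy or resection specimen". SAP 7.9.2 keeps the same restriction: "Proportion of patients with CR at 12 months who subsequently developed progressive disease in TA".

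The recurrence and durability endpoints (nos. 1, 6, 8 and 9) also require CR at 12 months.

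Three other parts of the CIP bear on this:

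- Section 9.10 applies the term progressive disease to the whole study, defines it as ESCC in any biopsy or resection specimen, and treats progression in the last four years as failing the durability endpoint.
- Section 9.4.1 classes patients with residual ESCN at month 12 as treatment failures and schedules their escape treatment in the 3 months (+/- 4 weeks) after that visit. Sections 9.4.1, 9.4.3 and 9.9 keep them in follow-up so that the secondary endpoints can be assessed.
- Section 6.2 reports on an earlier study: "The 12 patients with residual ESCN suffered a poorer prognosis. Fifty-eight percent (7/12 patients) developed progressive disease".

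**The concern.** The two progression endpoints do not together cover the cohort and the follow-up period. A patient with residual MGIN or HGIN at month 12 goes to escape treatment. If that specimen, or any biopsy up to month 60, is the first to show ESCC in the TA, the event is too late for no. 3 and the patient is outside the denominator of no. 7. Section 9.10 assigns such an event to a durability endpoint, but every durability endpoint excludes the patient.

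Following the plan exactly would give a late progression figure conditional on treatment success, reported against an objective that asks for the overall figure. The study has a single arm, so no comparator would expose the difference. If the missing analysis were added only after results were known, it would be open to suspicion of selective reporting.

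**Working it through.** **1. Coverage of the endpoints.** Which endpoint counts a first ESCC in the TA:

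| Time found | CR at 12 months | No CR at 12 months | Month 12 not assessed |
|---|---|---|---|
| To month 12 | no. 3 | no. 3 | no. 3 |
| After month 12 | no. 7 | none | none |

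The empty cells follow from the wording alone. The additional analyses in CIP 13.6 and SAP 7.11 do not fill them: the multivariate model concerns complete response, and the subgroup analyses name no progression outcome.

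**2. Patients affected.** CIP 13.2 expects CR of 80%-90% in 100 subjects. Non-responders number 100 x (1 - 0.80) = 20 down to 100 x (1 - 0.90) = 10. This is an upper limit, because section 9.10 also counts patients with ESCC before month 12 as treatment failures, and no. 3 has already taken them.

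**3. The earlier study (CIP 6.2).** Its figures reproduce: 7/12 = 58.3% (stated as 58%) and 4/78 = 5.1% (stated as 5%). One of the four was HGIN, so ESCC in the sustained-CR denominator is 3/78 = 3.8%. The histology of the 7 is not given, so the all-patient figure has to be shown as a range:

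- if 5 of the 7 were ESCC (the number treated non-endoscopically): (3 + 5)/(78 + 12) = 8/90 = 8.9%
- if all 7 were: (3 + 7)/90 = 10/90 = 11.1%
- if only 1 was: 4/90 = 4.4%, still above 3.8%

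The exact 95% confidence interval for 7/12 is 27.7% to 84.8%.

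**4. Projection to 100 patients.** Counted by no. 7 = 100 x CR x 3/78. Uncounted = 100 x (1 - CR) x r, where r is the late ESCC rate in non-responders. The documents do not give r for this trial. The values used are an assumed 20%, the lower confidence limit of 27.7%, and 58.3%. The share missed is in brackets.

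| CR | Counted | Uncounted, r = 20% | r = 27.7% | r = 58.3% |
|---|---|---|---|---|
| 80% | 3.1 | 4.0 (57%) | 5.5 (64%) | 11.7 (79%) |
| 90% | 3.5 | 2.0 (37%) | 2.8 (44%) | 5.8 (63%) |

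Half the late cases are missed when r = CR x (3/78)/(1 - CR). That is 15.4% at 80% CR and 34.6% at 90% CR.

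**The case against.** The strongest objections concern size and consequence.

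- **The earlier data are not like for like.** Section 6.2 calls them preliminary, with one pathology result pending and follow-up violations in 59% of patients. It uses progression loosely enough to include an HGIN case. It does not say that the 7 progressed after month 12, or spell out that residual ESCN means no CR at month 12. That study enrolled 9 ESCC patients among 96, whereas this trial excludes ESCC (CIP 8.4). This trial also sends failures directly to escape treatment. All of this stands, and 58% should not be carried over as a forecast.
- **Most late cases need not be missed.** A reader might infer that the endpoints omit the larger part of late ESCC. The documents do not establish that. At an assumed 20%, uncounted and counted cases are similar in number, and at 90% CR most are counted.
- **These patients are not hidden.** Each patient with residual ESCN at month 12 fails the primary endpoint. ESCC deaths enter no. 10, disease outside the TA enters no. 11, and adverse events are recorded regardless of relationship (CIP 11.2). CIP 13.6 lists use of escape treatment as a subgroup factor. This stands against any claim of concealment, but none of these gives a rate of ESCC in the TA for the whole cohort.
- **A plain 60-month proportion would be poorly defined.** Section 9.4.1 takes patients given non-endoscopic treatment off the protocol's endoscopy schedule, and death and withdrawal also need rules. This stands and shapes the fix.

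None of these points fills the empty cells in the coverage table.

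**Conclusion.** Wrong as written, and it should be fixed before analysis. The objective promises overall ESCC progression, and the endpoints cannot deliver it for up to 10-20 of 100 patients. This part rests on the wording and needs no assumption.

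Used as a measure of overall progression, the no. 7 rate is biased downward if late ESCC is more frequent in non-responders than in responders. The contrast in section 6.2 points that way but does not prove it for ESCC alone. On those counts the gap is 3.8% against 8.9% or 11.1%, depending on the unreported histology. In this trial about 2-4 cases would go uncounted at an assumed 20% and about 6-12 at 58%, with every subject assumed to have a month-12 status and no earlier ESCC among the non-responders. Whether the missed cases are the majority depends on the scenario.

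The primary endpoint and the sample size are unaffected. This is a descriptive secondary outcome, so the matter is important but not critical.

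**What to change.** Add one endpoint to CIP 5.2.2 and SAP 7.9.2 and name it as the measure for the overall ESCC progression objective: first ESCC in the TA in any biopsy or resection specimen, escape-treatment specimens included, from primary RFA to month 60, in all enrolled cohort subjects irrespective of CR at 12 months. Report it as cumulative incidence with a 95% confidence interval, with death as a competing event and censoring at withdrawal or last assessment. Also show results by 12-month status: CR, no CR, not assessed.

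State how the analysis handles patients given non-endoscopic treatment, since section 9.4.1 takes them off the endoscopy schedule. The rule matters most for those treated without ESCC having been shown. Keep nos. 3 and 7 as components, and align section 9.10 so that late progression in a patient without CR is assigned to an endpoint that can count it.

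The cost is revised wording in both documents and one extra table. Follow-up to study termination and central reading of specimens are already planned, though specimens are not assured for patients who leave the endoscopy schedule. The downside for the sponsor is a less favourable progression figure.

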6.1. Duration

Enrollment of up to 100 subjects is expected to take 12 months. Subject’s duration of involvement in the study is expected to be up to 60 months (estimated based on primary RFA plus 12 months of treatment phase and 48 months of follow-up). The overall study is expected to last a total of 6 years if enrollment is completed in a timely manner.

6.2. Rationale

This study design is a prospective, multi-center, non-blinded, single-arm (non-randomized), post-market study. This study design was selected given the desire to evaluate treatment efficacy (RFA) on a disease state (ESCN) with generally well understood natural history. Two recently published reports have evaluated the Barrx™ Flex Radiofrequency Ablation System for the eradication of ESCN (11, 18). Bergman et al. 2011 reported on 29 subjects (18 MGIN, 10 HGIN, and 1 ESCC) treated with circumferential RFA followed by focal RFA every 3 months until the complete histological eradication of MGIN or worse. Two energy applications were administered at 10 J/cm² or 12 J/cm², with and without cleaning of the coagulum between passes. The primary endpoint was complete response at 12 months, defined as the histological absence of MGIN, HGIN, or ESCC. The rate of complete response was 86% at 3 months after the primary RFA session and 97% at 12 months after the primary RFA session (11). Four strictures (14%) were reported, all dilated to resolution. The authors concluded that RFA was associated with a high rate of histological complete response for the eradication of ESCN with no neoplastic progression (11). Because the stricture rate was slightly higher than typically reported in studies assessing RFA for the treatment of Barrett's Esophagus, the authors concluded that technique and dose may contribute to stricture formation and proposed further evaluation of dosimetry to preserve the high rate of complete response while reducing the stricture rate (11).

The authors continued the study to a total enrollment of 96 subjects (45 MGIN, 42 HGIN, and 9 ESCC). In that analysis, the complete response rate was 73% after 3 months (1 RFA session) and 84% after 12 months. The stricture rate was 21%. However, when using a circumferential RFA dose of 12J/cm² with one application and no cleaning of the coagulum, the stricture rate was only 6%, with complete response rates of 65% and 82% at 3 months and 12 months respectively. This regimen had additional benefit of procedural simplicity. However, only a total of 17 patients were treated with this regimen (18).

Although preliminary, results for the long-term follow-up of this study will be shortly discussed. Sustained CR during 5 years follow-up was observed in 86% (67/78 patients). Recurrence occurred in 9% (7/78 patients, MGIN 5, HGIN 1). 5 were managed with RFA, one with ESD. Progression of baseline disease occurred in another 5% (4/78 patients; HGIN (n=1), sm-ESCC (n=3)); all were treated with ESD. Two progressor lesions were normally stained after Lugol's and with repeatedly negative biopsies, and were therefore left untreated. Later both lesions were considered suspicious for cancer and escape treatment was performed, with pathology assessment for one case showed submucosal cancer buried under normal epithelial cells. Pathology assessment for the second case is pending.

However, protocol violations during follow-up occurred in the majority of patients (59%) resulting in prolonged follow-up intervals, lesions left untreated or no adequate follow-up after detection of recurrent or progressive disease. This might have interfered with the results, and those might have been better with strict follow-up protocols.

The 12 patients with residual ESCN suffered a poorer prognosis. Fifty-eight percent (7/12 patients) developed progressive disease and were treated with either ESD (n=2) or non-endoscopic treatment (n=5), suggesting that RFA failures should directly be managed with an alternative treatment like EMR or ESD.

Therefore, to further assess the safety, effectiveness, and durability of the Barrx™ Flex Radiofrequency Ablation System for the eradication of ESCN, the current study will employ methods similar to the 2 studies reported above but with a consistent primary RFA dose of 12 J/cm² with one application and no cleaning of the coagulum, and with subsequent 5-years follow-up according to strict study protocols.

7. Product Description

7.1. General

The Barrx™ Flex Radiofrequency Ablation System uses radiofrequency (RF) energy to coagulate (ablate) the thin layer of diseased squamous epithelium of the esophagus. RF is used for the purpose of coagulation and ablation in many other target tissue sites. The heat generated by RF delivery results in tissue vaporization or coagulation. Specific to the esophagus, the study device has been evaluated extensively in the treatment of Barrett's esophagus, a glandular metaplastic disease of the esophagus related to gastroesophageal reflux disease.

There are two Barrx™ Flex Radiofrequency Ablation Systems, each with a specific role in the treatment of diseased esophageal epithelium.

Each part of the Barrx™ Flex Radiofrequency Ablation System is assembled in a Medtronic manufacturing facility. Each part of the process from the raw materials to the finished device is diligently controlled to ensure the quality and effectiveness of each product.

7.2. The Barrx™ Circumferential Radiofrequency Ablation System

The Barrx™ Circumferential Radiofrequency Ablation System includes an energy generator (Model 1190A-115A), ablation catheters (Model 32041-18, 32041-22, 32041-25, 32041-28, 32041-31), and sizing balloons (Model 3441C). The circumferential ablation catheters will be used for independent treatment or main treatment. The energy generator is used to inflate a sizing balloon positioned within the esophageal body, in order to measure the inner diameter of the targeted portion of the esophagus. Upon determination of the inner diameter size (mm), an appropriately sized ablation catheter is selected for ablation. The ablation catheter has a balloon at its distal end, wrapped with an electrode having tightly spaced bipolar electrode bands. The generator inflates this ablation catheter within the esophagus and delivers the controlled amount of RF energy to achieve the desired ablation effect. At

the recommended energy density and number of applications, the maximum depth of ablation in previous studies is the muscularis mucosae.

7.3. The Barrx™ Focal Radiofrequency Ablation System

The Barrx™ Focal Radiofrequency Ablation System (Model 90-9100, 90-9200, 90-9300: additional models may be used for the study after CFDA approval is obtained) consists of a similar energy generator and a cap-based electrode that is mounted on the distal end of an endoscope. The focal ablation catheters will be used for supplementary topical treatment. This device is introduced with the endoscope to provide more focally targeted ablation of small areas of disease, either primary or secondary therapy. The Barrx™ Focal Radiofrequency Ablation System is substantially equivalent to the Barrx™ Circumferential Radiofrequency Ablation System in terms of energy delivery and ablation depth, having the same electrode design. The difference is that the surface area is smaller, allowing more focal selective ablation of residual diseased tissue, and this device is attached to the endoscope, rather than to a balloon catheter.

7.4. Regulatory Approval in China

The Barrx™ Flex Radiofrequency Ablation System obtained CFDA approval in January 2015 for the following indication for use: The Barrx Flex System is indicated for the clinical treatment of lesions limited to the mucosa in the gastrointestinal tract, specifically flat intraepithelial neoplasia and Barrett's esophagus.

In this proposed clinical trial, the Barrx Flex RFA Generator will be utilized in accordance with the indications for use in the labeling for the device. All study device catheters are single use, disposable medical devices. See the Clinical Evaluation Report, REG-0023 and REG-0022 for additional information.

7.5. Product Training Requirements

Each Investigator participating in the clinical trial and the associated clinical study staff will receive training on the clinical protocol, IRB-approved ICF and additional training materials as per the study training plan, as well as hands-on training in the use of the Barrx™ Flex Radiofrequency Ablation System for the treatment of ESCN. All endoscopies will be observed by an expert from CICAMS. The tissue specimen review and histopathological interpretation will be centralized at CICAMS by expert pathologists who are the process developers, hence do not require additional training.

